7.1. PROHIBITED THERAPY AND THERAPEUTIC/DIAGNOSTIC PROCEDURES

None of the concomitant therapies and therapeutic/diagnostic procedures listed below are allowed during the study period (except those listed in **Section 7.2**):

- Anticancer agents such as cytotoxic chemotherapy small-molecule targeted agents, biological agents, immune response modifiers or hormonal therapy,
- Local therapies which could interfere with treatment (e.g. surgical excision or ablation of lesions are not permitted without Sponsor approval while subjects are receiving study treatment),
- Investigational drugs (other than study drugs) and devices,
- Radiation therapy (not including palliative radiotherapy at focal sites that covers $\leq 10\%$ of the bone marrow reserve),
- Herbal preparations/medications. Subjects should stop using herbal medications 7 days prior to first dose of study treatment,
- Concomitant moderate or strong systemic CYP3A4 inhibitors or inducers which are likely to significantly increase or decrease respectively encorafenib exposure and thus should not be used during this study (see **Section 17.5**).

If another therapy and/or therapeutic / diagnostic procedure has to be prescribed in the interests of the subject's health, the decision to discontinue the subject from the study should be taken by the Investigator.

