5.7. SUBJECT DISCONTINUATION REASONS

The reasons for a subject's premature discontinuation from the study may be the following (in all cases, available data will be retained for the safety analysis):

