5.7.1. Treatment Discontinuation for Individual Subject

Subjects may decide to stop participating in the study at any time for any reason without prejudice to their future medical care by the physician or at the institution. Wherever possible, the tests and evaluations listed for the End of Treatment visit and Safety Follow-up visit should be carried out and an effort should be made to continue follow-up.

If a subject decides to discontinue study treatment, he/she should be asked if he/she is willing to be contacted by telephone for monitoring of survival.

If a subject withdraws consent, the subject's data collected up to the date of consent withdrawal will be included in the analyses. The date, stated reason for and level of consent withdrawal should be documented. Any blood or tissue samples collected up to the date of withdrawal of consent will be analyzed, unless explicitly prohibited by the subject.

The Sponsor should be notified of all subjects' decision to discontinue study treatment and all study withdrawals through the designated e-CRFs in a timely manner.

Subjects meeting any of the following criteria must discontinue study drug treatment:

- **Subject decision to discontinue study treatment** (but request agreement to return for end of treatment assessments, safety follow-up assessments and/or survival follow-up).
- **Withdrawal of consent:** no further participation
- **Lost to follow up:** A subject will be considered as lost to follow up, if he/she did not attend a scheduled visit and for whom no news can be obtained after three documented attempts

with a minimum of 15 days between the first and the last attempt. This status must be dated at the latest as the database lock.

- **Investigator decision** in the subject's interest if an SAE occurs and is considered by the Investigator liable to threaten the health of the subject or if a serious disease occurs and necessitates the prescription of a medication incompatible with the pursuit of the study. The Sponsor should immediately be informed by phone or fax or email and a report explaining the discontinuation will be forwarded to him as soon as possible.
- **Progressive disease:** at any time (to be taken into account only for treatment discontinuation).
- **Unacceptable AE or toxicity** (related or not to the study treatment) or failure to tolerate the study treatment.

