5.7.2. Study Discontinuation for individual Subject

The subject may be considered discontinued from the study for the following reasons:

- Withdrawal of consent.
- Lost to follow-up.
- Death.
- Termination of the study by the Sponsor.

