8. ASSESSMENTS

8.1. EFFICACY ASSESSMENTS

Tumor response will be evaluated locally by the Investigator according to RECIST, v1.1 (**Section 17.6**).

All potential sites of tumor lesions will be assessed at screening, the following should be performed:

- A CT scan with IV contrast of chest, abdomen and pelvis is the preferred technique. If there is concern about radiation exposure, an MRI may be used instead of a CT.
- In subjects with a history of asymptomatic brain metastases, a brain MRI or CT scan
- If clinically indicated, a whole-body bone scan (i.e., if bone metastases are suspected or known at baseline). A whole-body bone imaging method may be used per local standard of care (e.g., Tc99m bone scan, fluorodeoxyglucose-positron emission tomography [FDG-PET], sodium fluoride-positron emission tomography [NaF PET] scan or whole-body bone MRI).

Skeletal lesions identified on a whole-body bone scan at baseline, which are not visible on the chest, abdomen, or pelvis CT (or MRI) scan should be imaged at baseline using localized CT, MRI, or X-ray.

As far as possible, the same method of assessment of each lesion should be used at screening and for all visits, for consistent comparison.

During the Main study period, all post-screening assessments should be performed every 6 weeks (± 7 days) from the first dose for the first 12 weeks of treatment; except for first tumor evaluation for which the time-window allowed is day 42 ± 7 days from first dose. Then, every 8 weeks thereafter until disease progression, subject decision, withdrawal of consent, initiation of subsequent anticancer therapy, subject is lost to follow-up, death or defined end of study as described in **Section 5.7**.

During the Study extension period, all assessments should be performed every 12 weeks (± 7 days), until disease progression, subject decision, withdrawal of consent, initiation of subsequent

anticancer therapy, subject is lost to follow-up, death or defined end of study as described in **Section 5.7**.

If a subject discontinues study treatment for reasons other than disease progression, tumor assessments must continue to be performed (as per local and central review) every 6 weeks (first 12 weeks) then every 8 weeks during the Main study period and every 12 weeks during the Study extension period (as per local review), until the start of new anti-cancer therapy, disease progression, death, lost to follow-up, subject decision or withdrawal consent.

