10.4. REPORTING OF PREGNANCY TO THE SPONSOR

Pregnancy occurring during the period between signing of the ICF but before any study treatment exposure is not to be reported to the Sponsor unless associated to an AE.

If pregnancy is suspected while the female subject is receiving study treatment, the study treatment(s) should be discontinued immediately until the result of the pregnancy testing is known. If pregnancy is confirmed, administration of study drug is to be discontinued immediately and the subject must be withdrawn from the study.

The Investigators must report to the Sponsor any on-treatment pregnancy of a female subject or a female partner of a male subject which occurs during study treatment and within the 30 days after the last dose administration of binimetinib or encorafenib and within the 6 months after the last dose administration of cetuximab.

On-treatment pregnancy (of female subject and female partner of male subject) must be reported to the Sponsor within 24 hours of the Investigator's knowledge using the investigational product pregnancy form.

Any pregnancy will be followed through to outcome, and the outcome must be reported to the Sponsor, including the infant's health status, using the pregnancy outcome report form.

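### Sections 7.1 and 10.4 allow or require study exit for reasons that Section 5.7.1 treats as stops of study drug and Section 5.7.2 does not list, so required follow-up could end early

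*Protocol*

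**What the plan says.** Protocol Section 7.1 lists prohibited therapies. If another therapy or procedure is needed for the subject's health, "the decision to discontinue the subject from the study should be taken by the Investigator".

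Section 5.7.1 covers nearly the same situation under Investigator decision: "if a serious disease occurs and necessitates the prescription of a medication incompatible with the pursuit of the study". That item stands in a list introduced by "Subjects meeting any of the following criteria must discontinue study drug treatment". Pregnancy is in the same list.

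Section 5.7.2 is the list of study exits: "The subject may be considered discontinued from the study for the following reasons". It has four entries: withdrawal of consent, loss to follow-up, death and termination by the Sponsor.

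Section 10.4 has study drug stopped when pregnancy is confirmed and adds that "the subject must be withdrawn from the study".

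Section 8.1 sets the rule after a treatment stop: "If a subject discontinues study treatment for reasons other than disease progression, tumor assessments must continue to be performed". It ends the assessments at new anticancer therapy, progression, death, loss to follow-up, subject decision or withdrawal of consent. Sections 9.1.10.2 and 9.2.5.2 have subjects who stopped treatment contacted by phone every 3 months for survival, subsequent anticancer therapy and progression after it.

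**The concern.** Stopping study drug and leaving the study have different consequences for the data. After a treatment stop, the protocol keeps collecting scans (up to the 8.1 end points) and survival status. After study exit, it collects neither. Sections 7.1 and 10.4 use the language of study exit for reasons that the dedicated sections handle as treatment stops. A site that follows 7.1 or 10.4 to the letter could end contact with a subject who is alive, has not withdrawn consent and is not lost to follow-up. Another site could apply 5.7.1 and continue.

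A subject who leaves in this way is censored for overall survival at the last date known alive. If the need for another therapy goes with clinical worsening, that censoring is informative and the Kaplan-Meier estimate is too favourable. With a single arm, there is no comparator in which a similar bias could offset it.

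**Working it through.** **1. The two triggers side by side**

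- *Another therapy needed.* Section 5.7.1 stops study drug. Section 5.7.2 does not list it. Section 7.1 speaks of leaving the study, at the Investigator's discretion.
- *Pregnancy.* Section 5.7.1 stops study drug. Section 5.7.2 does not list it. Section 10.4 speaks of leaving the study, without discretion.

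Section 6.5.1 also treats the start of subsequent anticancer therapy as a reason to end treatment, and 9.1.10.2 then collects that therapy and later progression. The protocol therefore expects subjects on subsequent therapy to remain in follow-up.

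**2. Which endpoints depend on the reading**

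*Prohibited anticancer therapy.* Section 8.1 already ends scans when it starts. SAP Section 14.1 excludes later scans from best overall confirmed response. SAP Table 12 row G (PFS) and Table 14 row F (duration of response) censor at the last adequate assessment before it. Study exit therefore adds no loss for these endpoints. It can lose overall survival, PFS2 (SAP Table 18) and data on further therapy.

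*Prohibited drug that is not an anticancer drug.* Section 8.1 requires scans to continue. Study exit would end them, so PFS and duration of response are exposed as well as overall survival, PFS2 and time to subsequent therapy (SAP Table 17).

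*Pregnancy.* The exposure is the same as for a non-anticancer drug. Follow-up of the pregnancy to its outcome is already required by 10.4.

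**3. Response confirmation**

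SAP Section 14.1 counts scans only before new antineoplastic therapy and no later than 30 days after the last dose. Scheduled scans are 6 weeks (42 days) apart for the first 12 weeks, then 8 weeks (56 days). On nominal dates, the scan after a first response counts only if the last dose came at least 42 − 30 = 12 days, or 56 − 30 = 26 days, after that first response. Outside that window, keeping the subject on study would not confirm the response.

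An unconfirmed response is classed as SD or NE (SAP Table 10, case 15) and stays in the fixed denominator (SAP Section 14.1). Either way it counts against the confirmed response rate: one subject is 1/90 = 1.1 percentage points.

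**4. Design figures**

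Inputs from Protocol Section 13.3: at least 12 of 40, then at least 37 of 90; rates 30% and 45%; stated type I error 1.6% and power 80%.

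Rejection probability = sum over x = 12 to 40 of P(X1 = x) × P(X2 ≥ 37 − x), with X1 ~ Bin(40, p) and X2 ~ Bin(50, p).

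- p = 0.30 gives 0.01606, which rounds to 1.6%.
- p = 0.45 gives 0.7985, which rounds to 80%.

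The plan's figures are reproduced, and nothing in this point changes them. The Clopper-Pearson interval for 37/90 is 30.8% to 52.0%, as stated. For 36/90 it is 29.8% to 50.9%, so one lost confirmation could matter at the boundary, in the direction of not rejecting.

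For illustration only, assume that a share d of would-be responders loses confirmation:

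- d = 1%: power 77.4%, type I error 1.37%
- d = 2%: power 74.7%, type I error 1.16%
- d = 5%: power 65.8%, type I error 0.68%

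The documents give no value for d. The illustration shows direction only.

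**The case against.** The strongest reply is that this is loose wording with no operative effect. Section 5.7 introduces both of its lists with "The reasons for a subject's premature discontinuation from the study may be the following", so leaving the study is used there for treatment stops too. The optional-biopsy footnote refers to stopping study drug for progression in the main flow chart, but to discontinuing the study in Table 25 and the extension flow chart, although progressed subjects clearly stay in survival follow-up. Sections 9.1.9 and 9.2.4 send all subjects into follow-up after the end-of-treatment visit. This reading is plausible. It does not remove the conflict, because a site is not told which reading applies, and 10.4 is worded as an obligation.

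A reader might also infer more than the documents support:

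- *That 7.1 removes subjects automatically.* It assigns a decision to the Investigator. Section 7.2.5.1 also allows short-term moderate CYP3A4 inhibitors after discussion with the Sponsor, which narrows the group.
- *That data are lost.* This is a risk under one reading, since other sections require follow-up.
- *That the primary result is inflated.* A lost confirmation lowers the confirmed response rate.
- *That a particular number of subjects is affected.* No count or rate is given.
- *That all PFS and duration-of-response censoring at new anticancer therapy comes from 7.1.* Section 8.1 and the SAP rules produce it regardless.

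**Conclusion.** The inconsistency is real and lies in operative text. Its reach is limited: overall survival, PFS2 and subsequent-therapy data for any subject taken off study under 7.1 or 10.4, and PFS and duration of response only where the reason is not anticancer therapy. The primary test is not threatened with a false positive, and N, type I error and power stand as stated.

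The size cannot be estimated from the documents; each subject affected is 1.1% of a 90-subject efficacy set. Bias in the survival estimates rests on two assumptions: that some sites act on the literal wording, and that the need for another therapy tracks prognosis. The second is reasonable for serious illness, is undocumented, and does not extend to pregnancy. The point is worth correcting because the remedy costs almost nothing.

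**What to change.** Reconcile Sections 7.1 and 10.4 with 5.7.1 and 5.7.2, so that these reasons end study treatment as 5.7.1 already provides and do not by themselves end study participation. Then state two things:

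- Tumour assessments continue until the end points already listed in Section 8.1, including new anticancer therapy and progression. Tying scans to 5.7.2 alone would contradict 8.1, because neither of those is a 5.7.2 reason.
- Survival contacts continue under 9.1.10.2 and 9.2.5.2 unless a 5.7.2 reason applies.

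No rule on which therapies or events stop treatment changes, and none is proposed here. The cost is about two sentences in an amendment, plus follow-up that the protocol already requires. Survival follow-up runs through the extension to the end of the study, so the correction is still useful after enrolment has closed.

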7.2. AUTHORIZED THERAPY, THERAPEUTIC AND DIAGNOSTIC PROCEDURES

In general, the use of any concomitant medication/therapies deemed necessary for the care of the subject is permitted, unless otherwise specified. Additional information regarding concomitant medications/therapies is provided in the Investigator's Brochures for encorafenib and binimetinib and the cetuximab locally approved labelling.

Subjects receiving any of the medications listed in **Section 17.5** must be used with caution carefully monitored for potentiation of toxicity due to any individual concomitant medication and may require dose titration of the drug substance. Investigators should use caution when prescribing concomitant medications, as clinical experience with these compounds in subjects with cancer is often limited. Investigators should contact the Sponsor or designee when they are unsure whether a drug should be prescribed to a subject in the clinical study. All concomitant medications/therapies, transfusions, procedures and dietary supplements must be documented in the e-CRF.

7.2.1. Skin Toxicity Treatments

Subjects should be treated for cetuximab-induced, encorafenib-induced and/or binimetinib-induced skin toxicity following the supportive care recommended guidelines for the management of these toxicities and prophylaxis measures referred to in **Section 17.1**.

7.2.2. Hand-Foot Skin Reaction Treatment

HFSR has been reported for encorafenib, so it is recommended that subjects are informed prior to starting study treatment to avoid activities that can cause friction to the hands and/or feet. In addition, supportive measures for prevention and/or management of HFSR should be instituted. Clinical judgment and experience of the treating physician should guide the management plan of each subject. Subjects receiving encorafenib should be treated for encorafenib-induced HFSR

following the supportive care recommended guidelines for the management of these toxicities (Section 17.3).

7.2.3. Anti-Diarrheal

Subjects should be treated for diarrhea as per institutional guidelines, and/or as indicated in the locally approved prescribing information, or for subjects receiving binimetinib, per the supportive care recommended guidelines for the management of binimetinib-induced diarrhea (Section 17.3).

7.2.4. Antiemetics

Prophylactic antiemetics should only be administered if the subject experiences nausea or vomiting and at the discretion of the Investigator. It is recommended that subjects use drugs that do not cause QT prolongation. Note that some antiemetics have a known risk for Torsade de Pointes (TdP) (Section 17.5).

7.2.5. Permitted Concomitant Therapy requiring Caution and/or Action

7.2.5.1. *CYP and UGT Substrates and Inhibitors*

Encorafenib is a reversible inhibitor of CYP2B6, CYP2C9, CYP3A4 and UGT1A1. It is also a time-dependent inhibitor of CYP3A4. Likewise, binimetinib is also a reversible inhibitor of CYP2B6. Permitted medications to be used with caution in this study include those that are sensitive substrates of CYP2B6, CYP2C8, CYP2C9, CYP2C19, CYP3A4, and UGT1A1 or those substrates that have a narrow therapeutic index (Section 17.5).

There is a potential for encorafenib to induce CYP3A4, which may reduce the effectiveness of hormonal contraception methods. Therefore, the use of at least one form of non-hormonal contraception is required during participation in this study (See Section 5.3 for use of contraception methods required for this study). Caution should be used in subjects receiving concomitant treatment with other drugs that are substrates of CYP3A4 as the efficacy of these drugs could be reduced when administered with encorafenib.

Encorafenib has been identified in vitro to be metabolized by CYP3A4 and to a lesser extent by CYP2C19. The use of strong inhibitors of CYP3A4 is prohibited. Concomitant use of moderate

CYP3A4 inhibitors while on study should be avoided. If use of moderate CYP3A4 inhibitors is unavoidable and no alternatives are available, short-term use (≤ 30 days) following discussion with the Sponsor may be permitted with accompanying dose reduction to one-half of the encorafenib dose prior to use of moderate CYP3A4 inhibitors (or as close as can be achieved without exceeding the target dose). The encorafenib dose that was taken prior to initiating the CYP3A4 inhibitor may be resumed after the inhibitor has been discontinued for 3 to 5 elimination half lives. Strong inhibitors of CYP2C19 should be used with caution when co-administered with encorafenib.

Binimetinib has been identified to be primarily metabolized by glucuronidation. It is advised that strong inhibitors of UGT1A1 should be used with caution when co-administered with binimetinib (**Section 17.5**).

Subjects should be closely monitored for the occurrence of AEs.

7.2.5.2. *Transporter Substrate and Inhibitors*

In vitro data showed that both encorafenib and binimetinib are substrates of the transporter P-glycoprotein (P-gp). Binimetinib is also a substrate of BCRP. Encorafenib is a BCRP inhibitor. Thus, the use of drugs that are known to inhibit or induce P-gp or BCRP should be used with caution. Encorafenib is also a potent inhibitor of the renal transporters, organic anionic transporter OAT1, OAT3 and organic cationic transporter (OCT) 2, and the hepatic transporter organic anion-transporting peptide (OATP1)B1 and OATP1B3. The co-administration of drugs that are known to be sensitive or narrow therapeutic index substrates of BCRP, P-gp, OAT1, OAT3, OCT 2, OATP1B1 and OATP1B3 should be used with caution (**Section 17.5**).

7.2.5.3. *Drugs with a Conditional or Possible Risk to Prolong the QT Interval and/or Induce Torsade de Pointes*

Investigators should use caution when administering encorafenib or binimetinib with concomitant medications with a known, conditional or possible risk to prolong the QT interval and/or induce TdP (**Section 17.5**). Subjects receiving such medications must be carefully monitored for potentiation of toxicity due to any individual concomitant medication, and may require dose titration of the concomitant medication.

8. ASSESSMENTS

8.1. EFFICACY ASSESSMENTS

Tumor response will be evaluated locally by the Investigator according to RECIST, v1.1 (**Section 17.6**).

All potential sites of tumor lesions will be assessed at screening, the following should be performed:

- A CT scan with IV contrast of chest, abdomen and pelvis is the preferred technique. If there is concern about radiation exposure, an MRI may be used instead of a CT.
- In subjects with a history of asymptomatic brain metastases, a brain MRI or CT scan
- If clinically indicated, a whole-body bone scan (i.e., if bone metastases are suspected or known at baseline). A whole-body bone imaging method may be used per local standard of care (e.g., Tc99m bone scan, fluorodeoxyglucose-positron emission tomography [FDG-PET], sodium fluoride-positron emission tomography [NaF PET] scan or whole-body bone MRI).

Skeletal lesions identified on a whole-body bone scan at baseline, which are not visible on the chest, abdomen, or pelvis CT (or MRI) scan should be imaged at baseline using localized CT, MRI, or X-ray.

As far as possible, the same method of assessment of each lesion should be used at screening and for all visits, for consistent comparison.

During the Main study period, all post-screening assessments should be performed every 6 weeks (± 7 days) from the first dose for the first 12 weeks of treatment; except for first tumor evaluation for which the time-window allowed is day 42 ± 7 days from first dose. Then, every 8 weeks thereafter until disease progression, subject decision, withdrawal of consent, initiation of subsequent anticancer therapy, subject is lost to follow-up, death or defined end of study as described in **Section 5.7**.

During the Study extension period, all assessments should be performed every 12 weeks (± 7 days), until disease progression, subject decision, withdrawal of consent, initiation of subsequent

anticancer therapy, subject is lost to follow-up, death or defined end of study as described in **Section 5.7**.

If a subject discontinues study treatment for reasons other than disease progression, tumor assessments must continue to be performed (as per local and central review) every 6 weeks (first 12 weeks) then every 8 weeks during the Main study period and every 12 weeks during the Study extension period (as per local review), until the start of new anti-cancer therapy, disease progression, death, lost to follow-up, subject decision or withdrawal consent.

Regardless of whether study treatment is discontinued, the following should be performed:

- Chest, abdomen, and pelvis CT (or MRI) scans
- Brain MRI or CT scan, if metastases were documented at baseline
- Skeletal lesions identified at baseline should continue to be imaged at subsequent scheduled visits using localized CT, MRI, or X-ray (using the same method used at baseline for all visits for any given lesion). After baseline, whole body bone scans need not be repeated, unless clinically indicated.
- Additional imaging evaluations may be performed if there is symptomatic evidence suggesting the possibility of disease progression based on clinical symptoms or physical examination at any time.

If off-schedule imaging evaluations are performed or if progression is suspected, every effort should be made to perform subsequent imaging evaluations in accordance with the original imaging schedule.

All CT scans should be performed with IV contrast. If a subject is known to have a medical contraindication to the contrast agent or develops a contraindication during the study, a CT scan without IV contrast of the chest and MRI with IV contrast, if possible, of the abdomen and pelvis may be performed. A CT scan of the brain, preferably with IV contrast, may be performed if MRI is contra-indicated.

Chest X-ray or ultrasound should not be used for tumor response assessments in this study.

Any lesions that have been subjected to loco-regional therapies (e.g., radiotherapy, ablation, etc.) should not be considered measurable, unless they have clearly progressed since that therapy. Previously treated lesions that have not progressed should be considered non-measurable and therefore, assessed as non-target lesions.

While FDG-PET scans are not required for this study, sites may perform combined PET/CT scans per their local standard of care, provided the CT is of similar diagnostic quality as a CT scan performed without PET, including the use of oral and IV contrast media. If acquired according to local standard of care, FDG-PET may be relied upon to document progressive disease (PD) in accordance with RECIST.

When possible, each center should have a designated radiologist responsible for the interpretation of scans and response evaluations for study subjects. At a minimum, a single radiologist should perform all evaluations for an individual subject.

Transmission for central review

All imaging data acquired for efficacy purposes during the Main study period will be transmitted to an imaging vendor for central review. Image transmission to the imaging vendor should be accomplished according to the imaging vendor manual. Full details of the central reading process are included in the Independent Review Charter.

